- j Laboratory and PSA analyses and the physical examination will need to be repeated if they are not within 21 days from randomization. Week 1 Day 1 cannot be longer than 3 weeks from randomization.
- k At this and each subsequent visit, the participant will return dispensed but unused study intervention to the investigator for recording on the CRF. Reasons for non-compliance will be recorded. A new supply of study drug sufficient to meet the dosing requirements of each participant will be dispensed.
- l Participants remaining on treatment beyond Week 52 will continue, where possible, to receive study intervention and assessments until the final evaluation of the randomized phase (i.e. at Week 52 for the last participant, see Section 4.4.1).
- m Prior to the final evaluation of the randomized phase of the study, all participants will go into Week 53 active follow-up or survival follow-up as applicable.
- n Each participant should complete an end of treatment visit after discontinuation of study intervention for any reason. All anti-cancer treatments after discontinuation study intervention in this study will be recorded on the CRF at the end of treatment visit. See Section 4.4.2 for more details once the date of the final evaluation of the randomized phase is determined.
- o Survival will be followed with contact with the participant and/or his caregiver every 3 months following the date of last treatment until the end of the study for participants treated with darolutamide, and until the final evaluation of the randomized phase for participants treated with enzalutamide (see Section 4.4.2).

2. Introduction

Prostate cancer is the second most common cancer and the fifth leading cause of cancer death among men worldwide ([World Health Organization 2017](#)). It is the most common non-cutaneous cancer and the second leading cause of cancer-related deaths in men in Europe ([World Health Organization 2008](#)) and the United States (USA) ([Hirsch et al. 2001](#)). The most significant morbidity of prostate cancer is bone metastases.

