- the proportion of participants with a decline in cognitive function during the 24-week period from baseline, as assessed by HVLT-R and TMT

The suggested sample size for the randomized phase is based on the assessment of TUG test as the primary endpoint; however, after the feasibility assessment, the appropriate endpoint and the time point and time frame of evaluation of the endpoint for this part of the study will be chosen and the sample size will be reassessed.

The study is designed to evaluate physical function, including balance and daily activity, in participants treated with darolutamide or enzalutamide. It will also evaluate, safety, cognitive function, fatigue, and survival in participants treated with darolutamide or enzalutamide.

Participants will receive treatment (darolutamide or enzalutamide) until toxicity or disease progression and receive assessments during treatment. The study will continue until at least 52 weeks after the initial dose of the last participant, unless the participant discontinued due to lost to follow-up, withdrawal, or death. All participants will be followed up for survival status until the end of the study unless participants withdraw their informed consent.

The primary analysis for the lead-in phase will be performed when the last participant in the lead-in phase has been on the study for at least 24 weeks, unless the participant discontinued due to lost to follow-up, withdrawal, or death.

The primary analysis for the randomized phase for the study will occur when last participant in the randomized phase of the study has been on the study for at least 24 weeks, unless the participant discontinued due to lost to follow-up, withdrawal, or death. A final analysis for the randomized phase for the study will occur when last participant in the randomized phase of the study has been on the study for at least 52 weeks, unless the participant discontinued due to lost to follow-up, withdrawal, or death.

No data monitoring committee, dose escalation committee, or similar review group will be used for this study. The study will be conducted only in the USA at approximately 20 sites.

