6.7 Intervention after the End of the Study

The study will continue until at least 52 weeks from the initial dose of the study intervention of the last participant randomized in the study, unless the participant discontinued due to lost to follow-up, withdrawal, or death.

All anti-cancer treatments after discontinuation of treatment with study intervention in this study will be recorded on the CRF.

At the end of study intervention for the individual participant, further therapy is at the discretion of the investigator. Participants treated with darolutamide who are clinically benefitting can continue to receive treatment.

The sponsor reserves the right to terminate access to study intervention, in particular if any of the following occur:

- a) the study is terminated due to safety concerns
- b) the participant can obtain medication used in this study as treatment from a government sponsored or private health program

7. Discontinuation of Study Intervention and Participant Discontinuation/Withdrawal

All participants who enter the study should complete all applicable study periods. Participants can be withdrawn from any study period at any time. Withdrawal from the intervention period alone does not constitute withdrawal from the study.

Participants will be followed up for survival status unless they withdraw their informed consent.

Participants will continue study intervention until intolerable toxicity or progressive disease.

Participants who withdraw from the intervention period for any reason are to be encouraged to remain on the study for follow-up of primary, secondary and other objectives (i.e., continue in the active follow-up and survival follow-up periods). Participants are expected to participate in follow-up unless they explicitly object. Withdrawal of consent to the intervention period should be documented in the participant's medical record. If the participant does not wish to be followed up further, this additional consent withdrawal for follow-up must also be documented.

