7.1 Discontinuation of Study Intervention

In rare instances, it may be necessary for a participant to permanently discontinue study intervention. If study intervention is permanently discontinued, the participant will remain in the study to be evaluated for 52 weeks.

See the SoA (Section 1.3) for data to be collected at the time of intervention discontinuation and follow-up and for any further evaluations that need to be completed.

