**Table 3 Study Populations for Analyses**

Population	Description
Enrolled	All participants who sign the ICF.
Full analysis set (FAS)	All enrolled participants or all randomized patients (for the randomized phase of the study). This population will be used for baseline and disposition summaries as well as for the analysis of secondary endpoints related to efficacy.
Safety population	All enrolled (or randomized for the randomized phase of the study) participants who received any quantity of study intervention, regardless of their eligibility for the study. The safety evaluation will be performed based on the study treatment actually received.  The safety population will be used for all baseline, exposure, physical function, cognitive function, daily function, and safety analyses. For the evaluation of each endpoint using an instrument or questionnaire, participants with baseline and at least one post-baseline assessment will be included.

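### Protocol 4.1, Section 7 and the schedule disagree on whether TUG continues after study drug is stopped, so the Week 24 primary measurement may be missed and the participant in effect scored as not worsened

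*Protocol*

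**What the plan says.** **After stopping drug, evaluation continues.** Protocol 7.1: "If study intervention is permanently discontinued, the participant will remain in the study to be evaluated for 52 weeks". The opening text of Section 7 says that those who leave the intervention period "are to be encouraged to remain on the study for follow-up of primary, secondary and other objectives", and adds: "Participants are expected to participate in follow-up unless they explicitly object".

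**Other text points elsewhere.**
- Protocol 4.1: "Participants will receive treatment (darolutamide or enzalutamide) until toxicity or disease progression and receive assessments during treatment".
- Section 7 names the route for continued follow-up as "i.e., continue in the active follow-up and survival follow-up periods". In Protocol Tables 1–1 and 1–2, active follow-up is the column that begins at Week 53.
- Table 1–2, footnote n: "Each participant should complete an end of treatment visit after discontinuation of study intervention for any reason". Footnote o: "Survival will be followed with contact with the participant and/or his caregiver every 3 months following the date of last treatment".
- The TUG row is marked at baseline, Weeks 12, 24 and 52, and from Week 53. It is blank at the end-of-treatment visit, as are the SPPB, accelerometry and cognitive rows. SAP Tables 8–1 and 8–2 show the same blanks, while Karnofsky score, laboratory tests, PSA, vital signs and physical examination are marked there.

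**Analysis.** The primary variable is worsening of at least 1 second at any time in the first 24 weeks (SAP 5.5.1). For each instrument, "participants with baseline and at least one post-baseline assessment will be included" (SAP Table 3). SAP 4.2 does not impute missing primary data, but plans a sensitivity analysis that sets missing TUG times to a worsening.

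**The concern.** Within the 24-week window, TUG is scheduled at only two post-baseline visits. A man who stops drug at Week 14 has an end-of-treatment visit at about Week 18 with no TUG, and then survival contacts counted from his last dose. Section 7.1 and Section 7 imply that he returns for Week 24. Section 4.1 and the schedule do not tell the site to bring him back. With about 20 sites, practice could differ.

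Stopping for toxicity is plausibly related to physical decline, and the trial's premise is that the two drugs differ in tolerability. Loss of the Week 24 test could therefore be informative and unequal between arms. A TUG that was not done cannot be recovered at analysis.

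**Working it through.** **1. What each passage gives the Week 14 stopper**

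| Source | Week 24 TUG done? |
|---|---|
| Protocol 7.1 | Yes, by implication; it then refers to the schedule for details |
| Section 7, opening text | Yes in intent, but by a route that the schedule starts at Week 53 |
| Protocol 4.1 | Assessments described as received while on treatment |
| Schedule columns | Week 24 sits under an intervention-and-observation heading; on or off drug not stated |
| Schedule footnotes | End-of-treatment visit, then survival contact; nothing on off-drug tests before Week 52 |

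**2. How the SAP then scores him**
- Stable at Week 12, Week 24 missing: he has one post-baseline TUG, so he is in the denominator. Nothing is imputed and no worsening is observed, so he is in effect not worsened.
- Stopped before Week 12 and never tested again: no post-baseline TUG, so he is excluded.

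**3. The plan's own sample size**

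Inputs from Protocol 9.2: 20% against 40%, one-sided alpha 10%, power 85%, drop-out 10%, about 120 randomized 1:1. With unpooled variance:

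n = (z₀.₉₀ + z₀.₈₅)² × (0.2×0.8 + 0.4×0.6) / 0.2² = 53.7, so 54 per arm. Then 108 / 0.9 = 120, which matches. Power at 54 per arm is 85.1%.

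**4. Illustration of the loss**

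Assumptions, none of them from the documents: 60% of each arm's 24-week worsening is already seen at Week 12; a share q of the arm stops between the two tests and has no Week 24 TUG; stoppers' late risk is m times the arm's average, with arm totals held at 40% and 20%.

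Late worsening is 0.4 × 0.40 = 0.16 (enzalutamide) and 0.4 × 0.20 = 0.08 (darolutamide). Observed rate = true rate − q × late worsening × m. Power is unpooled, 54 per arm, one-sided 10%.

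| q enza / daro | m | Enzalutamide | Darolutamide | Difference (points) | Power |
|---|---|---|---|---|---|
| 0 / 0 | – | 40.0% | 20.0% | 20.0 | 85.1% |
| 10% / 5% | 1 | 38.4% | 19.6% | 18.8 | 82.1% |
| 10% / 5% | 2 | 36.8% | 19.2% | 17.6 | 78.7% |
| 20% / 10% | 1 | 36.8% | 19.2% | 17.6 | 78.7% |
| 20% / 10% | 2 | 33.6% | 18.4% | 15.2 | 70.8% |

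For example, at 20% / 10% and m = 2: 0.40 − 0.20×0.16×2 = 0.336 and 0.20 − 0.10×0.08×2 = 0.184.

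**5. Dependence on the assumptions**
- Reverse the stopping (10% enzalutamide, 20% darolutamide, m = 1): 0.40 − 0.016 = 0.384 and 0.20 − 0.016 = 0.184. The difference is still 20.0 points.
- Take 60 per arm, pooled variance, half of the worsening seen by Week 12, and 10% loss in both arms: 38.0% against 19.0%, with power falling only from 87.2% to 85.3%.
- Under that second method, with 30–70% of worsening seen by Week 12 and darolutamide/enzalutamide losses from 5%/5% to 10%/30%, the difference is 13.0–19.7 points and power 64–87%.

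**The case against.** A reader might infer that the plan stops TUG when drug stops. The documents do not support that. Section 7 says that leaving the intervention period alone is not withdrawal from the study, and it names the primary objective in its follow-up rule. Section 7.1 promises 52 weeks of evaluation. Section 4.4.2 defines completion by the Week 52 evaluation, with exceptions only for loss to follow-up, withdrawal and death. The Week 1–52 columns cover observation as well as intervention, and 4.1 does not say that assessments occur *only* on treatment. This stands: loss of the Week 24 TUG is a risk under one reading, not a rule.

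The SAP also has a safeguard. If the missing-as-worsened analysis covers a missing Week 24, the Week 14 stopper would count as worsened. That stands in part. It is not the primary analysis, and the SAP does not say whether it covers a missing Week 24 after a stable Week 12 or restores men excluded for want of any post-baseline TUG.

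Finally, the stopping rates are assumed, and the table applies them after the 10% drop-out has already reduced each arm to 54. With equal loss and no other drop-out, power stays near the planned 85%. That stands, and it limits what the figures can show. The randomized-phase endpoint and sample size are also provisional until the lead-in is reviewed.

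**Conclusion.** The passages conflict on how the primary measurement is collected after discontinuation, and the schedule, to which 7.1 sends the reader, does not settle it. The SAP does not state how a man with a stable Week 12 and a missing Week 24 is classified; its rules in effect count him as not worsened.

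A reader might go further and conclude that the primary comparison is biased against showing a difference, or that it hides worsening in the less tolerated arm. The documents do not establish this. They give no rate, timing or arm difference for discontinuation, and the reversed case above leaves the difference unchanged. Size and direction are undetermined.

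Under the assumed pattern of more stopping on enzalutamide (10–20% against 5–10%, 60% of worsening seen by Week 12, late risk of stoppers one to two times average), the difference falls from 20 to about 15–19 points and power from 85% to about 71–82%. That potential loss justifies a clarification before the randomized phase opens. The stated sample size of 120 is not in dispute.

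**What to change.** 1. **Protocol 4.1:** delete the closing words that tie assessments to the treatment period.
2. **Schedule (Protocol Tables 1–1 and 1–2, SAP Tables 8–1 and 8–2):** add a footnote to the TUG, SPPB, accelerometry, cognitive, BFI and PHQ-9 rows: *All visits marked for this assessment through Week 52 are counted from Day 1 and are performed whether or not study intervention has been discontinued, unless consent to follow-up is withdrawn.* The note must refer to each row's own marked visits, because cognition has no Week 12 test and BFI and PHQ-9 are also due at Weeks 4 and 8.
3. **Protocol Section 7:** for participants who stop before Week 52, replace active follow-up with the remaining scheduled visits through Week 52.
4. **SAP 4.2 and 5.5.1:** state how a participant not worsened at Week 12 with Week 24 missing is classified in the primary analysis. Apply the missing-as-worsened sensitivity analysis to these participants and to those with no post-baseline TUG.

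Do not add an end-of-treatment TUG to the primary endpoint. On an any-time-in-24-weeks definition, it would give the arm with more stops extra chances to cross 1 second.

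The cost is document wording and the effort of bringing off-treatment participants back, which 7.1 already requires.

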4.1.1 Randomization

This is an open-label study; however, the specific intervention to be taken by a participant will be assigned using an IWRS. The site will need to access the IWRS prior to the start of study intervention administration for each participant. The site will record the intervention assignment on the applicable case report form (CRF), if required. Randomization will be stratified by age (<75, ≥75 years).

4.2 Scientific Rationale for Study Design

This study is designed to assess physical function, daily activity level, cognitive functions, and influence of secondary events in participants with CRPC treated with darolutamide and enzalutamide. The primary aim of this study is to evaluate the effects of treatment with darolutamide or enzalutamide on physical function as demonstrated by changes in balance, mobility, and cognitive function in participants with CRPC. Standardized assessments of physical function including the TUG and SPPB will be used to monitor participants' physical function on treatment (Belch et al. 2003). Each participant will also use an accelerometry device to measure daily physical activity. The cognitive function assessments included in this study are the HVLt-R, TMT, COWA, and FACT-Cog. Fatigue and depression will be assessed using the BFI and PHQ-9, respectively. Before the randomized phase, in the lead-in phase in participants treated with darolutamide, these parameters will be assessed for feasibility and clinical relevance. After assessment in approximately 30 evaluable participants, the parameters and endpoints will be assessed and selected accordingly. This will allow a re-evaluation of the study design and endpoints before the randomized phase and allow a re-estimation of the assumptions for the comparator and study arms.

4.3 Justification for Dose

In the ARAMIS Phase 3 study, it was demonstrated that a dose of 600 mg darolutamide bid is sufficient to achieve maximum decrease in PSA and to result in a significantly longer metastasis-free survival (MFS) compared to the placebo arm. Overall, a darolutamide dose of 600 mg bid is considered to have an optimal benefit-risk profile.

The enzalutamide dose was based on approved dosing in the USA for enzalutamide in this population.

4.4 End of Study Definition

4.4.1 Final evaluation of the randomized phase

The final evaluation of the randomized phase will be at least 52 weeks from the initial dose of the study drug of the last participant randomized in the study, unless the participant discontinued due to lost to follow-up, withdrawal, or death.

If the trial is stopped but benefits are observed for ongoing participants, options for treatment continuation will be discussed and agreed between the investigator, sponsor and the participants.

4.4.2 End of assessments / follow-up

A participant is considered to have completed the study if he has completed all periods of the study including the last visit or evaluation at 52 weeks, unless the participant discontinued due to lost to follow-up, withdrawal, or death.

For participants treated with darolutamide, at the time of the final evaluation of the randomized phase:

- If ongoing on study intervention, the participant can continue treatment until he meets the criteria for discontinuation (see Section 7). After discontinuation, the participant should complete an end-of-treatment visit and enter survival follow-up until the end of the study (defined in Section 4.4.3).
- If in survival follow-up, the participant can continue in survival follow-up until the end of the study (defined in Section 4.4.3).

For participants treated with enzalutamide, at the time of the final evaluation of the randomized phase:

- These participants should complete an end-of-treatment visit or a final survival follow-up, as applicable. All participants treated with enzalutamide will reach their final assessment. No data will be collected for participants treated with enzalutamide beyond this time.

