- g BFI is a 5 minute self-assessment tool that identifies fatigue in cancer participants over a 24-hour period.
- h The first TUG assessment is to be performed before the first dose (either during screening or Week 1 Day 1).
- i Once the baseline procedures are completed, the first administration of study intervention will be provided at the study center and the participant will be provided with additional medication to take as scheduled through the Week 4 visit. (Each participant will be instructed to bring any remaining drug back to the center at the Week 4 visit.)
- j At this and each subsequent visit, the participant will return dispensed but unused study intervention to the investigator for recording on the CRF. Reasons for non-compliance will be recorded. A new supply of study drug sufficient to meet the dosing requirements of each participant will be dispensed.
- k Participants remaining on treatment beyond Week 52 will continue, where possible, to receive study intervention and assessments until the final evaluation of the randomized phase (i.e. at Week 52 for the last participant, see Section 4.4.1).
- l Prior to the final evaluation of the randomized phase of the study, all participants will go into Week 53 active follow-up or survival follow-up as applicable.
- m Each participant should complete an end of treatment visit after discontinuation of study intervention for any reason. All anti-cancer treatments after discontinuation of study intervention in this study will be recorded on the CRF at the end of treatment visit. See Section 4.4.2 for more details once the date of the final evaluation of the randomized phase is determined.
- n Survival will be followed with contact with the participant and/or his caregiver every 3 months following the date of last treatment until the end of the study for participants treated with darolutamide (see Section 4.4.2).

Table 1–2 Schedule of Activities for the Randomized Phase (darolutamide, enzalutamide)													
Assessment	Screening	Randomization	Intervention + Observation Period									End of treatment visit (30 days after last dose) ⁿ	Survival follow-up ^{m,o}
			Week 1 Day 1 ⁱ	Week 4 ^k	Week 8	Week 12	Week 24	Week 38	Week 52	from Week 53: Active follow up every 3 months ^{l,m}			
Time window allowed	within 21 days prior to randomization		within 21 days after randomization	± 7 days	± 7 days	± 7 days	± 7 days	± 14 days	± 7 days	± 1 month	+ 1 month	± 1 month	

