8.3.1 Time Period and Frequency for Collecting AE and SAE Information

An AE (irrespective of causal relationship) not completely resolved at the end of the pre-defined collection period must be followed up until resolution (defined as chronicity, baseline grade or complete resolution) or until the investigator considers the event will not improve further.

All SAEs will be collected from the signing of the informed consent form (ICF) until 30 days after the last dose, at the time points specified in the SoA (Section 1.3).

All AEs will be collected from the signing of the ICF until the follow-up visit(s) at the time points specified in the SoA (Section 1.3).

Medical occurrences that begin before obtaining informed consent will be recorded on the medical history section of the case report form (CRF).

Medical occurrences that begin before the start of study intervention but after obtaining informed consent will be recorded on the AE section of the CRF.

Medical occurrences that started before but deteriorated after obtaining informed consent will be recorded as AEs.

All SAEs will be recorded and reported to the sponsor or designee immediately and under no circumstance should this exceed 24 hours, as indicated in Appendix 3 (Section 10.3). The investigator will submit any updated SAE data to the sponsor within 24 hours of it being available.

Investigators are not obligated to actively seek AE or SAE after conclusion of the study participation. However, if the investigator learns of any SAE, including a death, at any time after a participant has been discharged from the study, and he/she considers the event to be reasonably related to the study intervention or study participation, the investigator must promptly notify the sponsor.

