8.3.3 Follow-up of AEs and SAEs

After the initial AE/SAE report, the investigator is required to proactively follow each participant at subsequent visits/contacts. All SAEs and non-serious AEs of interest will be followed until resolution, stabilization, the event is otherwise explained, or the participant is lost to follow-up (as defined in Section 7.3). Further information on follow-up procedures is given in Appendix 3 (Section 10.3).

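### Section 4.4.2 bars all further enzalutamide data after the final evaluation with no safety exception, against the rules in 8.3.1 and 8.3.3 to follow open events to resolution, and it leaves the cut-off point undefined

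*Protocol*

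**What the plan says.** Protocol 4.4.2 treats the arms differently at the final evaluation of the randomized phase. Darolutamide participants may stay on treatment, then have an end-of-treatment visit and survival follow-up until the end of the study. For enzalutamide the rule is "These participants should complete an end-of-treatment visit or a final survival follow-up, as applicable". The section adds that all of them reach their final assessment, and closes with "No data will be collected for participants treated with enzalutamide beyond this time".

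The safety sections make no distinction by arm:

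- Protocol 8.3.1 collects SAEs from consent to 30 days after the last dose. An adverse event still open when its collection period ends "must be followed up until resolution (defined as chronicity, baseline grade or complete resolution"), or until the investigator expects no further improvement. The section also requires prompt notification of a related SAE that the investigator learns of after discharge from the study.
- Protocol 8.3.3 states "All SAEs and non-serious AEs of interest will be followed until resolution, stabilization, the event is otherwise explained", or the participant is lost to follow-up.

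The randomized-phase schedule (Protocol Table 1–2) has the column "End of treatment visit (30 days after last dose"), with a window of plus 1 month and no minus. Its footnote n returns the reader to 4.4.2: "See Section 4.4.2 for more details once the date of the final evaluation of the randomized phase is determined". Footnote l lets participants beyond Week 52 continue "to receive study intervention and assessments until the final evaluation of the randomized phase". Footnote o runs survival follow-up "until the final evaluation of the randomized phase for participants treated with enzalutamide".

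**The concern.** A site with an unresolved fracture or SAE in an enzalutamide participant at the last contact has two instructions that cannot both be met: keep following and recording it, or record nothing more. If it obeys 4.4.2 literally, the outcome of that event stays open in the database. The same event in a darolutamide participant would be followed under 8.3.1 and 8.3.3 with nothing in 4.4.2 to stop it.

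The second difficulty is timing. If collection stops on the date of the final evaluation, a participant dosed up to that date has no post-dose SAE period, and his end-of-treatment visit falls after data collection has closed. Comparing safety between the arms is a secondary objective, with falls, fractures and hypothyroidism named as events of interest in the protocol, so completeness of follow-up should not depend on the arm.

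**Working it through.** The plan gives no figure to reproduce. The check sets the rules side by side and counts the days of the SAE window left uncovered.

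**Step 1: follow-up to resolution.** The rule for unresolved events in 8.3.1 operates after the collection period has ended, so 4.4.2 cannot be reconciled with it by saying that 4.4.2 merely ends collection. The rule in 8.3.3 ends only with resolution, stabilization, another explanation or loss to follow-up; reaching the final evaluation is not on that list. Wherever the cut-off in 4.4.2 falls, an event open at the last contact is covered by one rule and barred by the other. The duty to notify related SAEs learned of after discharge meets the same bar. This part of the conflict does not depend on how the cut-off is read.

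**Step 2: the 30-day SAE window.** Uncovered days = 30 minus the days from last dose to the cut-off, and not less than 0.

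| Reading of the cut-off | Days from last dose to cut-off | Uncovered days |
|---|---|---|
| Completion of the end-of-treatment visit as scheduled | at least 30 | 30 − 30 = 0 |
| Date of the final evaluation, participant still on drug | 0 | 30 − 0 = 30 |
| Participant already in survival follow-up, more than 30 days after last dose | more than 30 | 0 |

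The text supports both of the first two readings. For the earlier date: 4.4.2 introduces its instructions as applying at the time of the final evaluation, and footnotes l and o end assessments and enzalutamide survival follow-up there. For the later date: the same bullet asks for an end-of-treatment visit before it closes collection, and Table 1–2 does not allow that visit before day 30. Footnote n does not settle the matter, because it refers back to 4.4.2. Protocol 6.1 adds a further gap: enzalutamide is supplied by commercial prescription, so a participant may stay on it, and the documents do not say what then counts as his last dose.

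**Step 3: how many.** About 120 participants randomized 1:1 gives 120 / 2 = 60 on enzalutamide. The documents do not state how many would be on drug, or have an open event, at the final evaluation. The range is 0 to about 60.

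**Step 4: reach into the analyses.** Under 4.4.1 the final evaluation is at least 52 weeks after the first dose of the last randomized participant. The primary endpoint covers 24 weeks and is not affected. The SAP (5.5.5) counts treatment-emergent events to 30 days after the last dose in both arms but gives no data cut-off for the between-arm tables.

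**The case against.** Three stronger conclusions are tempting, and the documents support none of them.

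*The 30-day SAE window is lost in the enzalutamide arm.* A reader might infer this from the closing sentence of 4.4.2 alone. The sentences before it require an end-of-treatment visit and speak of a final assessment, which is the nearest thing the cut-off can refer to. With the visit timed as in Table 1–2, the window is covered in full. A count of participants losing it, such as 18 to 42 from an assumed 30% to 70% of 60 still on drug, rests on a share that the documents do not give, and becomes 0 on this reading. A participant who stays on prescribed enzalutamide has arguably not started a post-dose period at all. This objection stands: the timing is an ambiguity, not a proven contradiction.

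*The adverse event comparison is biased.* The final analysis (Protocol 9.4 and 9.5, SAP 5.4) is triggered when the last randomized participant reaches 52 weeks, the same milestone as the final evaluation. A darolutamide participant still on drug then also has no post-dose days. No later between-arm analysis is described, and nothing says that later darolutamide data enter the comparative tables. This stands too, although no stated cut-off rules it out.

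*Sites must abandon open SAEs.* Section 4.4.2 governs study data, not care. The notification duty in 8.3.1 remains, and Protocol 10.3.4 gives a paper or telephone route for new or updated SAE reports after the electronic tool is closed. These provisions suggest that SAE reporting was not meant to end. They do not remove the conflict: they leave the wording of 4.4.2 as it is, and they do not cover non-serious events of interest or other unresolved adverse events. The statement in 8.3.1 that investigators need not actively seek events after participation ends does not release them from following events already known.

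Finally, the enzalutamide arm exists only if the randomized phase goes ahead, which limits the practical reach.

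**Conclusion.** The point holds for follow-up of open events. The blanket stop in 4.4.2 contradicts the arm-neutral rules in 8.3.1 and 8.3.3 on every reading, and it applies to one arm only. The consequence is incomplete safety follow-up in the comparator arm if the sentence is applied as written.

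On the 30-day SAE window the finding is narrower: the cut-off is undefined, and the loss per participant still on drug is between 0 and 30 of 30 days according to the reading. The number of participants concerned is unknown, from 0 to about 60. The upper end assumes both the stricter reading and that everyone in the arm is still on enzalutamide. There is no effect on the primary endpoint. An effect on the between-arm adverse event tables cannot be excluded, but is not demonstrated. The sponsor should correct this because the rules conflict and the correction is cheap.

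**What to change.** Reconcile Protocol 4.4.2, 8.3.1, 8.3.3 and Table 1–2 with its footnotes l, n and o:

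1. Limit the closing sentence of 4.4.2 to functional, questionnaire, PSA and survival data.
2. Define the cut-off as completion of the end-of-treatment visit or of the final survival contact, whichever applies. Say which date counts as the last dose for a participant who stays on prescribed enzalutamide.
3. State that 8.3.1 and 8.3.3 continue to apply in both arms to events open at that contact.
4. State in the SAP that the between-arm adverse event tables use the same data cut-off for both arms.

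No extra collection period is needed for participants who continue enzalutamide outside the study, since no section asks for one. The cost is protocol and SAP wording, plus limited safety follow-up of events still open in the enzalutamide arm.
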